3.4.2 Secondary Efficacy Endpoint Analyses

3.4.2.1 Secondary Efficacy Endpoints

Endpoints 1, 2, 3, and 4 are key secondary endpoints to be considered for studywise Type I error control.

1. Worsening from baseline in EDSS at last visit during the RCP.

A subject will be considered to have a worsening in overall EDSS score if one of the following criteria is met:

- a. Worsening of 2 or more points in EDSS score for subjects with baseline score of 0.
 - b. Worsening of 1 or more points in EDSS score for subjects with baseline score of 1 to 5.
 - c. Worsening of 0.5 points or more in EDSS score for subjects with baseline score of 5.5 or more.
2. Change from baseline in low-contrast visual acuity binocular score measured by low-contrast Landolt C Broken Rings Chart, at last visit during the RCP.
 3. Cumulative total active MRI lesions (new Gd-enhancing or new/enlarging T2) during the RCP.
 4. Number of NMO/NMOSD-related in-patient hospitalizations. In-patient hospitalization is defined as more than an overnight stay
 5. Annualized attack rate (total number of AC-determined NMO/NMOSD attacks normalized by person-years) during any exposure to MEDI-551.

3.4.2.2 Handling of Dropouts and Missing Data

Missing values of the secondary efficacy endpoints due to dropout or missing data will be handled as follows:

1. For worsening from baseline in EDSS endpoint, missing values will be considered as 'worsening' according to non-responder imputation (NRI) rule.
2. For low-contrast visual acuity endpoint, the last non-missing value will be considered for analysis.

3.4.2.3 Secondary Efficacy Endpoint Analyses

Secondary endpoints 1 through 4 presented in Section 3.4.2.1 for AQP4-IgG seropositive cohort will be analyzed as follows:

- Treatment effect for secondary efficacy endpoint based on EDSS worsening will be assessed using a logistic regression model with treatment and baseline EDSS as

explanatory variables. The percentage of subjects meeting the endpoint, odds ratios, p-value, and 95% CIs of the odds ratios will be presented.

- The treatment effect for the low-contrast visual acuity measured by change from baseline in low-contrast Landolt C Broken Rings Chart binocular scores will be assessed using an analysis of covariance model using treatment and baseline Landolt C Broken Rings Chart binocular score as explanatory variables.
- The treatment effect for the secondary efficacy endpoints based on the cumulative number of active MRI lesions and number of NMO/NMOSD-related in-patient hospitalizations will be tested using Negative Binomial regression with treatment as an explanatory variable.

Similar analyses will be performed for the ITT population by extending the above-mentioned models to include an indicator variable for serostatus as well.

See Section Appendix 3 for details regarding Type I error control.

Annualized attack rate (total number of AC-determined NMO/NMOSD attacks normalized by person-years) during any exposure to MEDI-551 will be summarized descriptively. See Table 3.3.3-1 for definition of person-years.

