4.8.3.3 Secondary Efficacy Analyses

Secondary endpoints 1 through 4 presented in Section 2.2.2 for AQP4-IgG seropositive cohort will be analyzed as follows:

- Treatment effect for secondary efficacy endpoints based on EDSS worsening will be assessed using a logistic regression model with treatment and baseline EDSS as explanatory variables. The percentage of subjects meeting the endpoints, odds ratios, p-value, and 95% CIs of the odds ratios will be presented.
- The treatment effect for the low-contrast visual acuity measured by change from baseline in low-contrast Landolt C Broken Rings Chart binocular scores will be assessed using an analysis of covariance model using treatment and baseline Landolt C Broken Rings Chart binocular score as explanatory variables.
- The treatment effect for the secondary efficacy endpoints based on the cumulative number of active MRI lesions and number of NMO/NMOSD-related in-patient hospitalizations will be tested using Negative Binomial regression with treatment as an explanatory variable.

Similar analyses will be performed for the ITT population by extending the above mentioned models to include an indicator variable for serostatus as well.

See Section 4.8.9 for details regarding Type I error control.

Annualized attack rate (total number of AC-determined NMO/NMOSD attacks normalized by person-years) during any exposure to MEDI-551 will be summarized descriptively.

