2.3 Treatment Assignment and Masking

Randomized-controlled Period

Prior to randomization, subjects will be stratified based on AQP4-IgG serostatus (determined at screening) and region (Japan vs non-Japan). Within each stratum, subjects will be randomized in a 3:1 ratio to receive either MEDI-551 300 mg or placebo at Day 1 and 15.

[figure not shown]

Figure 2.3-1 Study Flow Diagram

AC = Adjudication Committee; AQP4-IgG = aquaporine-4 immunoglobulin G; FU = follow-up; IV = intravenous; max = maximum; min = minimum; NMO/NMOSD = neuromyelitis optica/neuromyelitis optica spectrum disorders; OLP = Open-label Period; RCP = Randomized-controlled Period; Q26W = every 26 weeks; SFP = Safety Follow-up Period; yr = year

Open-label Period

All eligible subjects will receive open-label MEDI-551 300 mg every 26 weeks. However, subjects randomized to placebo during the RCP will receive an additional 300 mg MEDI-551 dose at Day 15 of the OLP to maintain a total initial dose of 600 mg. To protect masking, subjects randomized to MEDI-551 during the RCP will receive a placebo infusion at Day 15.

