2.4 Sample Size

Study CD-IA-MEDI-551-1155 is being planned to detect a target relative reduction of 60% in risk for time from Day 1 to onset of an adjudicated NMO/NMOSD attack on or before Day 197 with 90% power and $\alpha = 0.05$ (two-sided). A total of 67 AC-determined NMO/NMOSD attacks are required for the ITT population. Subjects will be randomized in a 3:1 ratio to receive either MEDI-551 or placebo within both AQP4-IgG seropositive and seronegative strata. The stratification ratio is anticipated to be approximately 80:20 with higher allocation to the seropositive cohort. If the sero-positive cohort has 80% of the attacks, the study will have approximately 82% power to detect the target relative reduction of 60%.

Two hundred and fifty-two subjects will be randomized. This sample size is based on a blinded review of the attack rate for the first 78 subjects to complete the RCP and on a simulation based on these subjects that indicates a 90% probability of achieving the required 67 AC-determined attacks with 252 subjects.

Within each AQP4-IgG stratum, randomization will also be stratified by region (Japan vs non-Japan). The number of Japanese subjects will be determined primarily by feasibility and will not depend on a minimum number of NMO/NMOSD attacks to be observed from Japanese subjects.

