3.4.1.3 Primary Efficacy Analysis

The following are the null and alternative hypotheses associated with the primary endpoint:

$$H_{01}: HR^+ = 1 \text{ vs } H_{11}: HR^+ \neq 1,$$

$$H_{02}: HR^{ALL} = 1 \text{ vs } H_{12}: HR^{ALL} \neq 1,$$

where HR^+ indicates the hazard ratio of AC-determined NMO/NMOSD attack for MEDI-551 relative to placebo in AQP4-IgG seropositive subjects. HR^{ALL} denotes the same quantity for the ITT population. The treatment effect in the seropositive cohort will be defined as the relative reduction in HR^+ ; ie, $100 \times (1 - HR^+)$. A value of $HR^+ < 1$ or a positive value of relative reduction will indicate the efficacy of MEDI-551 compared to placebo in the seropositive cohort. Similar interpretations will hold for HR^{ALL} . For the current study, the target treatment effect of 60% implies a hazard ratio (HR) of 0.4.

For the AQP4-IgG seropositive cohort, the treatment effect will be assessed using the Cox proportional hazards model with treatment indicator (MEDI-551 or placebo) as an explanatory factor; whereas for the ITT population, the model will also include serostatus as an additional explanatory factor. The HR of MEDI-551 versus placebo will be estimated together with its associated 95% CI. The SAS PROC PHREG will be used for fitting this model. Subjects who complete the Day 197 visit of the RCP or discontinue the study before Day 197 for reasons other than an AC-determined NMO/NMOSD attack will be censored in this model at the time of the Day 197/discontinuation visit.

An indicator variable for Japan versus non-Japan region will not be included in the Cox regression model due to the low number of anticipated Japanese subjects. An evaluation of consistency of treatment effect in Japanese subjects with that observed in the global study will be determined.

The data cutoff date for the primary analysis will be when the last subject completes the discontinuation visit following the 67th AC-determined attack, or after all subjects complete the RCP if 67 AC-determined attacks do not occur, or when the last subject completes the discontinuation visit following discontinuation of enrollment upon recommendation of the DMC based on evidence of efficacy and safety. Subjects who are in the RCP when a total of 67 AC-determined NMOSD attacks have occurred, or when enrollment is discontinued upon

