4 MULTIPLICITY ADJUSTMENT

The study is designed to strongly control the overall 2-sided Type I error rate of $\alpha = 0.05$ based on the Bonferroni-based chain procedure ([Bretz et al, 2009](#); [Millen and Dmitrienko, 2011](#)). The primary null hypothesis will be hierarchically tested first at $\alpha = 0.05$ in the AQP4-IgG seropositive cohort, and, if significant, it will be further tested in the ITT population at $\alpha = 0.05$. If and only if the treatment group comparison is statistically significant within the ITT population, secondary hypotheses will be tested. Null hypotheses for the 4 key secondary endpoints will follow the same sequential testing strategy as the primary analysis (testing within seropositive subjects first, followed by the ITT population if the comparison

within seropositive subjects is statistically significant). Each secondary hypothesis will be initially tested based on the Bonferroni method at $\alpha = 0.05/4 = 0.0125$. If the null hypothesis for a particular secondary endpoint is rejected across both the seropositive and the ITT populations, the Type I error saved will be propagated equally to other non-rejected sets of secondary null hypotheses. The testing procedure will be repeated until all null hypotheses are rejected or no further null hypothesis can be rejected. Details are described in Appendix 3.

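### The acuity ANCOVA pools one residual variance under 3:1 allocation, so its confidence interval will be somewhat too narrow if MEDI-551 prevents attacks that affect vision

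*SAP*

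**What the plan says.** SAP 3.4.2.3 states that the acuity effect will be "assessed using an analysis of covariance model using treatment and baseline Landolt C Broken Rings Chart binocular score as explanatory variables". Protocol 4.8.3.3 specifies the same model: "assessed using an analysis of covariance model using treatment and baseline Landolt C Broken Rings Chart binocular score". For the ITT population both documents add a serostatus indicator. Neither names a robust, Welch-type or arm-specific variance for this endpoint. SAP 3.1 says that model-based estimates will be shown with two-sided 95% confidence intervals and p-values.

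On allocation, SAP 2.3 says: "Within each stratum, subjects will be randomized in a 3:1 ratio to receive either MEDI-551 300 mg or placebo". On size, SAP 2.4 says: "Two hundred and fifty-two subjects will be randomized", and "The stratification ratio is anticipated to be approximately 80:20 with higher allocation to the seropositive cohort".

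Three provisions let an attack reach this endpoint. Ophthalmology is examined at Assessment Visits (Protocol 4.3.1.3). Subjects with an adjudicated attack may leave the randomized-controlled period for the open-label period (Protocol 3.1.1.3). The last non-missing acuity value is the one analysed (SAP 3.4.2.2). The score taken during an attack can therefore be the analysed score.

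**The concern.** An ANCOVA with no stated variance structure estimates one residual variance. In this trial the change in acuity can be thought of as a mixture: little change in subjects whose vision is not hit by an attack, and a loss of variable size in those whose vision is. The arm with more attacks then has the larger variance. If the drug works, that arm is placebo, which is only a quarter of the sample.

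The two effects compound. The pooled variance is weighted three to one towards the less variable arm, while the true variance of the difference is driven mainly by the small, more variable arm. With equal allocation the error would cancel.

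At stake is the stated precision of the acuity effect. The bias in the standard error arises when the drug is effective, which is when this interval would be read and relied on. The concern is not about the point estimate.

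**Working it through.** **The plan's own figures.** The documents give no SD, power or coverage for acuity, so only the primary-endpoint planning can be reproduced. With hazard ratio 0.4 ("For the current study, the target treatment effect of 60% implies a hazard ratio (HR) of 0.4"), 3:1 allocation, two-sided 0.05 and 90% power, the formula in SAP Appendix 1 gives [(1.960 + 1.282)/ln 0.4]² × 16/3 = 66.75, so 67 attacks, as stated. With 80% of these (53.6) in the seropositive cohort, power is 82.8%, against about 82% stated.

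**Attack rates by arm.** SAP Appendix 1 assumes 1.5 attacks per year on seropositive placebo, 0.6 on MEDI-551, and 0.54 years of follow-up.
- Placebo: 1 − exp(−1.5 × 0.54) = 55.5%.
- MEDI-551: 1 − exp(−0.6 × 0.54) = 27.7%.

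Protocol Appendix 9 gives a 50% chance of 67 attacks with 227 subjects, which implies a blinded pooled rate of 67/227 = 29.5%. Split at hazard ratio 0.4, that is 48.4% and 23.2%. On either basis placebo has about twice the proportion with an attack.

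**Error in the standard error.** Let R be the placebo to MEDI-551 residual variance ratio, v the MEDI-551 variance and n₁ the MEDI-551 sample size, with placebo n₁/3.
- True variance of the difference: (v/n₁)(3R + 1).
- Pooled-model variance: (v/n₁)(R + 3).
- k = true SE / model SE = √[(3R + 1)/(R + 3)].
- Coverage of the nominal 95% interval = 2Φ(1.96/k) − 1.

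| R | k | Coverage at 3:1 |
|---|---|---|
| 1.0 | 1.000 | 95.0% |
| 1.1 | 1.024 | 94.4% |
| 1.2 | 1.047 | 93.9% |
| 1.5 | 1.106 | 92.4% |
| 1.7 | 1.139 | 91.5% |

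At 1:1 both variances are proportional to R + 1, so k = 1 for any R.

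**What R could be (assumed).** Scale the non-attack residual SD to 1. Let p be the attack probability, q the share of attacks that affect the binocular score, and m and s the mean and SD of the loss. The arm variance is 1 + pq·s² + pq(1 − pq)·m².
- q = 0.25, m = s = 1: placebo 1.258, MEDI-551 1.134, R = 1.11.
- q = 0.5, m = s = 4: placebo 8.65, MEDI-551 5.12, R = 1.69.
- q = 0.1, m = s = 0.5 to 1: R = 1.01 to 1.05, coverage 94.9% to 94.7%.

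Over q = 0.25 to 0.75 and m = s = 1 to 4, R is 1.11 to 1.69 and coverage 94.4% to 91.5%. With s set to half of m on the same grid, coverage is 94.6% to 92.2%.

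**Simulation of the ANCOVA.** Seropositive arms of 50:151 and 42:126 were used, with 10% to 100% of attacks affecting vision, mean loss 5 to 30 characters and noise SD 4 to 8 (all assumed). R was 1.04 to 1.69 and coverage 94.9% to 91.1%. An ITT example (63:189) had R = 1.34 and coverage 92.9%. With no drug effect, coverage was 95.2%. With 1:1 allocation and R = 1.55, it was 94.9%.

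**The case against.** The strongest objection is that the size is assumed, not derived. The documents give no acuity SD. The endpoint is binocular, whereas most optic neuritis criteria can be met by loss in one eye, and myelitis, brainstem and brain attacks need not touch acuity at all. If few attacks move the binocular score, or move it little, coverage is 94.7% or better. This stands. A reader might infer that the interval certainly covers only 91% to 94%; the documents do not support that as an unconditional statement.

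A reader might also infer that the 0.0125 starting level is compromised, since SAP section 4 says: "Each secondary hypothesis will be initially tested based on the Bonferroni method". That does not follow. If the drug does nothing, the arms have equal variance and the test keeps its size. Inflation would need equal means with unequal variances. In the mechanism described here the same attack-related loss produces both differences, so they appear and vanish together.

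It is tempting to extend the point to the pain and SF-36 ANCOVAs. Those endpoints are exploratory, and no calculation shows that attacks make their change scores more variable by arm.

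Finally, the 55.5% and 27.7% rates belong to the plan for 212 subjects, while the arm sizes come from the maximum of 252. Together they imply about 82 attacks, in a trial that stops at 67. This is a fair correction with little effect: coverage depends on the variance ratio and the allocation, hardly on the sample size, and the blinded rate gives the same picture.

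**Conclusion.** The point holds in conditional form. As written, the acuity ANCOVA uses a pooled variance under 3:1 allocation. If MEDI-551 prevents attacks that lower and spread the score, the model-based standard error is too small. A variance ratio of 1.0 to 1.1 makes no practical difference. A ratio of 1.2 to 1.7 understates the standard error by roughly 4% to 12% (1 − 1/k) and brings 95% CI coverage from about 94% down to 91.5%.

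The conclusion rests on three things: the usual meaning of an ANCOVA with no variance structure stated, the planned reduction in attacks, and an assumed share and size of attack-related binocular loss. It concerns the precision reported for one key secondary endpoint when the drug works. It is a modest defect, worth correcting because the correction is cheap and should be fixed before unmasking.

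**What to change.** In SAP 3.4.2.3, keep the ANCOVA mean model for acuity and add one sentence that bases the confidence interval and test on one of the following, in both the seropositive and the ITT models:
- HC3 robust standard errors; or
- a residual variance per arm (PROC MIXED with REPEATED / GROUP=treatment, and Kenward-Roger or Satterthwaite degrees of freedom).

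Name one of the two. Across the assumed range where the plain ANCOVA covered 91.7% to 94.2% in simulation, HC3 gave 94.5% to 95.3% and arm-specific variance 94.5% to 95.2%.

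The cost is a slightly wider interval if the variances differ, and essentially none if they do not. Neither option is perfect. Where a few subjects have very large losses, coverage stays a little below 95%: about 93.9% in one set of simulations, and 92.6% to 93.5% with HC3 in the most extreme scenarios tried.

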3.4.2.4 Subgroup Analyses of Secondary Efficacy Endpoints

Consistency of treatment effect based on the secondary efficacy endpoints in each of the following subgroups will be assessed based on the analysis methods described above for the ITT population.

- Sex (male vs female)
- Baseline EDSS (< 5 or ≥ 5)
- Number of prior NMO/NMOSD relapses (< 2 or ≥ 2)
- Disease duration category (< 5 years, ≥ 5 years)

The nominal p-value and 95% CIs of treatment effect will be provided for each subgroup analysis. Forest plots will be generated to visually present the consistency of treatment effect in different subgroups with overall treatment effect.

3.4.3 Healthcare Resource Utilization

Healthcare Resource Utilization (HCRU) information is collected for this study to quantify the impact of disease and treatment on the subject's medical facility visits. Information will be collected throughout the RCP and the OLP on all NMO-related HCRU visits as presented in Table 3.4.3-1.

Table 3.4.3-1 Healthcare Resource Utilization Information

Parameter	Frequency
Ambulance transport	Total number of times since the last visit
Hospitalization (intensive care)	Total number of days since the last visit
Hospitalization (general care)	Total number of days since the last visit
Emergency Room/Department visits	Total number of times since the last visit
Visits to primary healthcare physician	Total number of times since the last visit
Other healthcare visits (eg, physiotherapist)	Total number of times since the last visit
Home visit from a physician	Total number of times since the last visit
Home visit from a nurse	Total number of times since the last visit

For ambulance transport, the total will be derived for each subject by summing the total number of times since the last visit over the entire RCP and OLP separately. This total will be used for analysis. Similar totals will be derived for other parameters.

3.4.3.1 Analysis of Healthcare Resource Utilization

The total for each of the above HCRU-defined parameters will be summarized descriptively for each treatment group and separately for the RCP and OLP.

3.5 Patient Reported Outcomes

3.5.1 Pain Scale

Eleven-point numerical rating scales will be used to capture a subject’s pain scores for pain experienced in the eyes, upper back, lower back, arms, and legs, respectively, where 0 = no pain and 10 = worst pain imaginable. The subject will be asked to rate the pain he/she has experienced over the last 7 days at each specified location separately.

3.5.1.1 Analysis of Pain Scale

Actual value and change from baseline of the pain scores for each body location (eyes, legs, arms, upper back, and lower back) will be summarized descriptively over all visits during RCP and OLP. The pain score averaged over all locations will be summarized.

Treatment effect for pain based on change from baseline at the last visit of the RCP will be tested using analysis of covariance models using treatment and baseline pain NRS scores as explanatory variables. Last non-missing value during RCP will be used for this analysis.

Another supportive analysis will be implemented using mixed effects model repeated measures (MMRM) approach. In this model, change from baseline will be dependent variable; baseline pain score, treatment and time will be used as independent variables. An

interaction term of treatment and time will also be included. The Kenward-Roger approximation will be used to estimate denominator degrees of freedom and adjust standard errors. The treatment difference will be obtained with LSMEAN statement from SAS PROC MIXED for the treatment difference at a specified visit. An unstructured within subject error covariance matrix will be used for this model. Subjects' last value during RCP will be aligned with next closest scheduled visit in order to use all information available.

3.5.2 SF-36 Health Survey

The SF-36 Health Survey measures 8 dimensions of a subject's functional health and well-being and also provides 2 summary scores that characterize a subject's mental and physical health status. Two versions of this instrument (two recall periods, 4-weeks [standard] or 1-week [acute]) will be used for this study. The acute version will only be used at 'attack assessment visit' and 'attack follow up visit' during the RCP. The results from this version will be listed only. The standard version will be used at all visits and will be analyzed as described below. The SF-36 domain scores and physical and mental component summary scores will be calculated by Optum™.

3.5.2.1 Analysis of SF-36 Health Survey

Actual value, change and percent change from baseline of SF-36 scores will be summarized descriptively over all visits during RCP and OLP.

Treatment effect based on SF-36 PCS will be tested using an ANCOVA model using treatment and baseline SF-36 PCS score as explanatory variables. Similar analysis will be done for SF-36 MCS and the 8 remaining domains.

Another supportive analysis for PCS and MCS change scores during RCP will be implemented using mixed effects model repeated measures (MMRM) approach as described in section 3.5.1.1.

